2.2 BACKGROUND

Immune-mediated thrombotic thrombocytopenic purpura (also known as aTTP) is a life-threatening, thrombotic microangiopathy characterized by severe thrombocytopenia, microangiopathic hemolytic anemia, and organ ischemia. It is an ultra-orphan disease with an annual incidence reported to be about 3 cases per million people in the US (6, 7).

It is caused by inhibitory autoantibodies to vWF-cleaving enzyme ADAMTS13 that result in a severe deficiency in the activity level of the enzyme. Severe deficiency (<10%) of ADAMTS13 enzyme activity has been recognized as a biomarker specific for iTTP and is used in the acute and long-term management of patients with iTTP (8).

Von Willebrand factor, a key protein in hemostasis, plays a pivotal role in the recruitment of platelets to sites of vascular injury. More than 90% of circulating vWF is expressed by endothelial cells and secreted into the systemic circulation as ultra-large vWF (ULvWF) multimers. Under high shear stress conditions such as in arterioles and capillaries, the platelet-binding A1 domain of the ULvWF multimers interact spontaneously with the glycoprotein Ib-IX-V receptor on platelets. In healthy individuals, ULvWF multimers are immediately cleaved into smaller, regular-sized multimers by the vWF-cleaving protease ADAMTS13. This prevents ULvWF interaction with platelets and limits microthrombus formation. When there is severe ADAMTS13 deficiency, ULvWF released from the endothelium are not cleaved appropriately, leading to vWF-dependent platelet aggregation eventually resulting in microvascular thrombosis (9). The consumption of platelets in these microthrombi results in thrombocytopenia, one of the clinical feature of iTTP, and may present with muco-cutaneous bleeding symptoms such as epistaxis, bruising, petechiae, hematuria, and gastrointestinal bleeding (10, 11).

Prior to the availability of caplacizumab, episodes of iTTP were associated with an acute mortality of 10–20% and thromboembolic morbidities such as myocardial infarction and cerebrovascular accident. In addition, tissue ischemia caused by microvascular thrombosis may result in multiorgan dysfunction including renal dysfunction. Most patients have very high levels of lactate dehydrogenase (LDH) as a result of the combination of hemolysis and tissue ischemia. Elevations of serum troponin I and troponin T are common (12, 13).

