- If there is persistent thrombocytopenia, defined as lack of a sustained platelet count increment or platelet counts of $<50 \times 10^9/L$ and a persistently raised LDH level ($>1.5 \times$ upper limit of normal [ULN]) despite five days of treatment.
- If there is clinical evidence of new or progressive ischemic organ injury (worsening of presenting signs and symptoms or appearance of new signs and symptoms such as but not limited to neurologic manifestations [seizures, sudden onset numbness or weakness of the face, arm, or leg especially on one side of the body, mental status changes including confusion, trouble speaking, or understanding speech, sudden visual impairment, sudden difficulty walking, loss of balance or coordination, sudden severe headache with no known cause], cardiac manifestations such as chest pain with or without electrocardiogram (ECG) changes suggestive of myocardial ischemia, increasing troponin, renal manifestations such as worsening serum creatinine at any time after starting therapy, TPE may be started at Investigator discretion at any point during the study, including the first 24 hours and cplacizumab and IST continued.

If participant needs TPE:

Recommend TPE with plasma (eg, fresh frozen plasma, solvent detergent/viral-inactivated plasma, cryosupernatant) at 1 to $1.5 \times$ estimated plasma volume. TPE should be performed daily according to standard site practice and continued at least for 2 days after the platelet count normalization ($\geq 150 \times 10^9/L$). Of note, TPE with 1 to $1.5 \times$ estimated plasma volume may be spread over multiple sessions within 24 hours. Tapering of TPE after platelet count normalization, defined as reducing its frequency to less than once per day, is strongly discouraged and if considered, should be discussed with the Medical Monitor.

Treatment plan for continued therapy with cplacizumab and IST regardless of hospitalization status:

If there is response to initial therapy:

- The participant will continue cplacizumab 10 mg (11 mg in US and Canada) SC daily until sustained ADAMTS13 normalization ($\geq 50\%$) at 2 consecutive visits after platelet count normalization defined as $\geq 150 \times 10^9/L$, or for 12 weeks, whichever occurs first. The maximum treatment duration of cplacizumab is 12 weeks for the presenting episode.

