8.1.2 Clinically significant TTP events

Clinically significant TTP events will be assessed at the time points indicated in the SoA ([Section 1.3](#)).

Date of onset, severity, and outcome of following parameters will be collected:

- Neurological
- Cardiovascular
 - Elevated cardiac troponins I (cTnI) (value and local upper limit of reference range)
 - Acute myocardial infarction (ECG finding)
 - Conduction abnormality (ECG finding)
 - Repolarization abnormality (ECG finding)
 - Heart failure (severity)
 - Other (to be specified)
- Renal
- Exacerbation of TTP
- Relapse of TTP
- Death due to TTP
- Other (to be specified)

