- The values resulting from these derivations will be the values used for the graphical representation of platelet, LDH and ADAMTS13 activity from Day 4.

Consecutive laboratory assessments are considered as 'consecutive visits' for efficacy endpoints.

A participant could potentially have missing laboratory assessment data, however, remission could still be confirmed at a subsequent laboratory value. In the case there is inadequate information to determine the remission status of a participant by the end of the study, the participant will be treated as not having achieved remission.

Clinical evidence of new or progressive ischemic organ injury

Clinical evidence of new or progressive ischemic organ injury is defined as any presence of following clinically significant iTTP event:

- Neurological event
- Elevated cardiac troponins
- Acute myocardial infarction
- Conduction abnormality
- Repolarization abnormality
- Heart failure
- Clinically significant renal event

which will be identified from the checkboxes in the "Clinically Significant TTP Event" eCRF form.

Exacerbation of TTP, Relapse of TTP and Other event will not be considered as clinical evidence of new or progressive ischemic organ injury.

Sustained Clinical Response

Sustained Clinical response is defined by the concomitance of the 3 following criteria for at least 2 consecutive visits (starting from D2):

- platelet count $\geq 150 \times 10^9/L$
- LDH $< 1.5 \times ULN$
- no clinical evidence of new or progressive ischemic organ injury

Remission

Remission is defined as (1) a sustained Clinical response (see above) associated with (2) Clinical remission or (3) Complete ADAMTS13 Remission, whichever occurs first, and defined as:

- Clinical remission: No TPE (*Plasma Exchange* form) and no anti-VWF therapy (Caplacizumab treatment) for ≥ 30 days (from the date that Clinical Response is achieved).
- Complete ADAMTS13 Remission: The attainment of ADAMTS13 activity level $\geq 50\%$ for at least 2 consecutive visits (starting from D2).

Time to event

For each of below time to event, in case of no observation of the event or death, the censoring date will be defined as the last non-missing value of the analyzed parameter (platelet count, LDH....) if any, else as the start date of treatment (defined as first caplacizumab administration [whatever marketed or study IMP]).

- Time to platelet count response will be calculated as follow:

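### SAP 5.4 counts any flagged organ event as new or progressive injury, so a persisting presenting abnormality can block Remission, while ischemic injury recorded only under Other is never counted

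*SAP*

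**What the plan says.** Protocol 9.2.2 and SAP 3.2.1 define Clinical Response in the same three parts: a platelet criterion, an LDH criterion, and the absence of ischemic organ injury that is new or progressive, over at least two consecutive visits. Both routes to Remission start from a sustained Clinical Response, so the third part feeds the primary endpoint.

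SAP 5.4 turns the third part into a programming rule. The injury is "defined as any presence of following clinically significant iTTP event", and seven items follow: neurological event, elevated troponins, acute myocardial infarction, conduction abnormality, repolarization abnormality, heart failure and clinically significant renal event. They are read from the checkboxes of the form for clinically significant TTP events. The section then adds: "Exacerbation of TTP, Relapse of TTP and Other event will not be considered as clinical evidence of new or progressive ischemic organ injury".

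The protocol explains the phrase only once, among the criteria for starting TPE in section 4.1: "worsening of presenting signs and symptoms or appearance of new signs and symptoms such as but not limited to" a series of neurological, cardiac and renal examples.

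On data collection, Protocol 8.1.2 states: "Date of onset, severity, and outcome of following parameters will be collected". Its list has an Other entry with free specification twice, once under Cardiovascular and once at the top level. The schedules in Protocol 1.3.2 and 1.3.3 have these events assessed from Day 1 (baseline) through every follow-up visit.

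**The concern.** The endpoint text asks whether injury is new or getting worse. The coding rule asks whether a box is ticked. The two differ for a participant who arrives with organ involvement that then stays stable or leaves a residue. The rule can call that participant a non-responder on the strength of the presenting illness.

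The rule also errs the other way. An ischemic injury that fits none of the seven boxes and is written under Other cannot count, however new it is. The rule is therefore not simply conservative: one half can lower the responder rate and the other can raise it. In a single-arm study whose result is one estimated proportion, the classification rule determines that result, and here it departs from the endpoint both documents define.

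**Working it through.** **Step 1: rule against definition.**

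| Question | Endpoint (Protocol 9.2.2, SAP 3.2.1) | Coding (SAP 5.4) |
|---|---|---|
| Must the injury be new or worse? | Yes | No; presence is enough |
| Troponin | Protocol 4.1 speaks of a rising value | A box for an elevated value |
| Onset, severity, outcome | Collected (Protocol 8.1.2) | Not used |
| Other, specified in free text | Collected (Protocol 8.1.2) | Top-level Other excluded by statement; Cardiovascular Other not among the seven items |

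**Step 2: can presenting injury reach the form?** Yes. Events are assessed from Day 1. Exclusion criterion E 09 (Protocol 5.2) removes severe neurological or cardiac disease and troponin above 5 x ULN, so milder involvement remains eligible. Protocol 2.2 says: "Elevations of serum troponin I and troponin T are common". Under Protocol 8.1.3 and 8.1.4 the investigator decides whether an abnormality is a clinically significant TTP event. That is a test of significance, not of newness.

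**Step 3: when does it block, and when does it only delay?** SAP 5.4 needs the three criteria together at two or more consecutive visits from Day 2.
- If the event clears and is no longer flagged, a later pair of visits can qualify, so response is delayed.
- If it stays flagged, no pair qualifies and Remission is blocked.
- Which of these applies is partly undefined. SAP 5.4 treats consecutive laboratory assessments as consecutive visits, whereas injury comes from an event form. Protocol 8.1.2 lists no end date, and the SAP does not say at which visits a Day 1 record counts.

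**Step 4: when does Other produce a false responder?** For the primary endpoint all of these must hold: the ischemic injury is recorded only under Other, no TPE is given, and the platelet and LDH criteria are met.

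**Step 5: the plan's own figure.** Inputs are n = 55 and an assumed 70% responder rate (Protocol 9.4, SAP 4), the latter from 0.85 x (1 - 0.18) = 0.697. The Wilson lower bound is

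[p + z²/(2n) - z·√(p(1-p)/n + z²/(4n²))] / (1 + z²/n), with z = 1.96.

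Rounding up to whole participants, 36, 39, 42, 44 and 47 of 55 give 52.3%, 57.9%, 63.7%, 67.6% and 73.8%. These match the published rows of 52, 58, 64, 68 and 74%.

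**Step 6: effect per participant.** 1/55 = 1.8 points. Starting from 39/55:

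| Participants reclassified as non-responders | Rate | Lower bound |
|---|---|---|
| 0 | 39/55 = 70.9% | 57.9% |
| 1 | 38/55 = 69.1% | 56.0% |
| 2 | 37/55 = 67.3% | 54.1% |
| 3 | 36/55 = 65.5% | 52.3% |

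For a wrongly blocked participant, the rule reports the lower row when the higher one is right. For an ignored Other event, the rule reports the higher row when the lower one is right. The counts of 1 to 3 are illustrations, because the documents give no frequency.

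**The case against.** The strongest reply is that the rule is narrower than it looks. Only events the investigator judges clinically significant are ticked, so a minor stable troponin elevation need not appear. The form may be an event log completed once at onset. A presenting event would then carry a Day 1 date and might never count later. CRF completion instructions are a separate document (Protocol 10.1.7) and could restrict entries to new or worsening findings. The open-ended wording in Protocol 4.1 belongs to the TPE criteria, not to the endpoint. The exclusion of Other is a pre-specified choice, and new ischemic injury is itself a listed reason for TPE, which already makes a participant a primary non-responder.

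Much of this limits the size of the problem; it does not remove it. The significance filter does not test newness, and neither document supplies the missing condition or the event-to-visit rule. The endpoint uses the same phrase that Protocol 4.1 explains. The TPE argument makes a false primary responder less likely but does not exclude one, since TPE in that situation is discretionary.

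A reader might also infer three stronger points that the documents do not support:
- That resolving injury blocks Remission. It does not, because any later qualifying pair of visits suffices.
- That the primary rate falls by some stated range, such as up to 10 points. No frequency is given, and an affected participant matters only if otherwise a TPE-free responder.
- That Clinical Response on treatment is hit harder because troponin is often raised early. That period can last 12 weeks, and two later visits are enough.

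**Conclusion.** The point stands in a limited form. SAP 5.4 does not implement the endpoint that Protocol 9.2.2 and SAP 3.2.1 define. A presenting abnormality that stays flagged can block Clinical Response and Remission without being new or progressive, and a new ischemic injury recorded only under Other is never counted. The two errors act in opposite directions.

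The size is 1.8 points of the responder rate, and about 1.9 points of the Wilson lower bound, per participant reclassified from a base of 39/55. The number affected is unknown and could be zero. The first half depends on how the eCRF form is completed and carried forward, which the documents do not show. The exclusion of Other is stated outright and does not depend on the form.

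A reader might note that three wrongly blocked participants put the lower bound at 52.3%, under the 54% printed below the sample-size table, and call that a failed study. The documents do not support this reading: SAP 3.1 sets no success criterion or test, and the 54% is a footnote from a post-hoc analysis of another trial's placebo arm.

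**What to change.** In SAP 5.4:
1. Count a listed event against Clinical Response only from its onset, if that is after first caplacizumab, or from its recorded worsening, if it was present at baseline. Do not count it at later visits where it is recorded as stable, improving or resolved. Without that last condition, the stable residue of a post-dose event would go on counting as new.
2. State how event records map to the laboratory-based consecutive visits, using onset date, severity and outcome. Protocol 8.1.2 does not establish that severity is recorded at each visit, so also say what is assumed where a visit has no status.
3. List unresolved presenting events separately.
4. Before database lock, have the medical team classify Other entries, cardiovascular and top-level, as ischemic or not, without sight of responder status, and count the ischemic ones.
5. Keep the any-presence rule as a sensitivity analysis, so that its effect on the primary rate is visible.

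The cost is SAP wording, some added programming and a brief medical review. The listed fields are already collected, and no change to treatment or visits is involved.
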